19.5. APPENDIX 5: EXIT QUESTIONNAIRE

Introduction: Thank you for participating in this study. We are really grateful for your willingness to help and volunteer for a study that aims to provide better wheezing treatment for our children in the future. Please take a moment to give us your feedback relating to the 3 biomarkers that were tested in this study as well as some comments on what you think the future definitive study should entail?

Question 1: How satisfied are you with this whole 1-year follow-up period study?

Very Dissatisfied	Dissatisfied	Neutral	Satisfied	Very Satisfied
				

Question 2: As a parent would you be interested in having the biomarker-based approach for your child in the future?

Yes	No	Maybe
		

Question 3: Did the study's 1-year follow up period help you change your mind on the 3 biomarkers (blood eosinophil count, FeNO and atopic sensitisation) being used in clinical settings for personalising treatment?

Not at all	Slightly	Moderately	Quite a lot
			

Question 4: Would you recommend this approach to other parents with children experiencing the same wheezing conditions?

Not at all	Maybe	Recommend	Highly recommend
			

Question 5: What else would you like to see in the future clinical trial? Would you change anything on the current process? What was good, what was not good?

Comment:

Survey's ending message: "Thank you for participating in our survey!"

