5. STUDY'S AIM AND OBJECTIVES

AIM: To obtain pilot data to test the hypothesis that aeroallergen sensitisation (confirmed by a wheal formation with a diameter ≥ 3 mm after a skin prick test is performed), FeNO (offline method) ≥ 10 ppb and a peripheral blood eosinophil count $\geq 300/\mu\text{l}$, alone or in combination, can predict future wheezing exacerbations in preschool children as well as response to treatment with inhaled corticosteroids, as a preliminary to a large, randomised controlled trial. Also, that these tests are acceptable to families.

OBJECTIVES:

- To recruit 100 preschool children with a history of wheeze, aged one to five years old, and determine atopic status, peripheral blood eosinophil count (point of care test) and FeNO (offline method).
- To evaluate the feasibility and acceptability of these tests
- To categorize the children according to the biomarkers tested and assess whether any or all, alone or in combination, predict future wheezing exacerbations as well as determine the clinical outcome over one year
- To obtain parents' and doctors' insights into whether the biomarkers mentioned above could be used in a future intervention study.

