In the event that a child has had their ICS treatment discontinued, we will record whether this was because the treatment was ineffective (treatment failure) or if the child was so well that the family or GP did not wish to continue (treatment success or spontaneous improvement). If an additional medication is prescribed, or the child is referred to secondary care, this will be considered as treatment failure. When the study ends, participants' parents/carers will be invited to a face-to-face focus group interview, or a one-to-one interviews, or remotely through Microsoft Teams, depending on their availability at the end of the study period. The focus group and one to one interviews will utilise a semi structured questionnaire, to provide qualitative feedback on the acceptability of the 3 biomarker tests. In addition, a separate focus group for doctors and nurses will be conducted to assess the feasibility of the 3 biomarker tests being used in clinical practice. They will be given all the information regarding the study as well as the study's patient information sheet. Those agreeing to take part, will sign a consent form. They will be attending either a face-to-face focus group interview, or a one-to-one interview, or remotely through Microsoft Teams, depending on their availability. A semi structured questionnaire will be utilised. Where possible a second independent researcher will sit in the focus groups discussion and interviews to ensure there is no bias. The conversations from the focus group and one to one interviews will be transcribed and coded into themes. We will utilise an external company for transcribing the conversations called 1st Class. <https://www.1stclass.uk.com/>

The focus group and one to one interviews will be audio recorded, transcribed and put into themes to conduct an inductive thematic analysis. 25% of the transcripts will be

double coded by an independent researcher, experienced in qualitative research to ensure that the correct themes have been used and to ensure that there is no bias. The focus group and one to one interviews will be used to assess the acceptability and feasibility of measuring biomarkers in primary care and using them to help determine management of preschool wheeze.

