In addition, we will ask them to fill in a very short electronic questionnaire after the study is finished, to check their perspective and acceptability on these biomarkers being used to guide children's therapy in the future (Appendix 5: Exit Questionnaire).

The whole duration of this study is expected to be 20-21 months, with 1-year follow-up for each patient included.

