10. END OF STUDY

The end of the study will be when the last of the 100 participants completes his follow-up period of 12 months with his/her last study visit. The anticipated finishing date is December 2023.

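### The exit questionnaire yields no acceptability figure for any single test, is completed about 12 to 21 months after first testing, and its Question 3 has no direction

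*Combined protocol and SAP*

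**What the plan says.** Section 5 makes acceptability part of the aim ("Also, that these tests are acceptable to families") and an objective in its own right ("To evaluate the feasibility and acceptability of these tests"). Section 5.1 names it again as part of the benefit the study will generate. No rate, threshold or criterion is attached to it.

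Two sources of evidence from parents are described in section 6 and repeated in section 7.1:

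- **Focus groups or one-to-one interviews**, semi-structured, at the end of the study, "to provide qualitative feedback on the acceptability of the 3 biomarker tests". They are transcribed and analysed thematically, with a quarter of transcripts double coded.
- **The exit questionnaire.** The protocol states "we will ask them to fill in a very short electronic questionnaire after the study is finished". Its purpose is "to check their perspective and acceptability on these biomarkers being used to guide" children's therapy in the future.

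The exit form in Appendix 5 has four closed questions and one free-text question. Question 3 asks the parent whether the follow-up year did "help you change your mind on the 3 biomarkers", taken together, on four options from *Not at all* to *Quite a lot*. The monthly form in Appendix 4 has no acceptability item. Section 11 lists no summary or analysis of acceptability.

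**The concern.** The three procedures ask very different things of a small child: tidal breathing into a bag, skin pricks with five allergens and two controls, and a finger prick for blood. Families may well accept one and dislike another. Section 5 also frames the hypothesis as the biomarkers alone or in combination, so a later trial might use fewer than three. A single pooled answer does not tell its designers how each test was received.

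Timing adds to this. A child's distress and a parent's willingness to repeat a test are best reported close to the event, and nothing quantitative is asked then. Question 3, the one closed item that mentions the biomarkers by name, does not record whether opinion moved for or against them.

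**Working it through.** The documents give no acceptability figure to reproduce. The check is an item-by-item reading of Appendix 5 against the objective, followed by two short calculations.

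**1. What each exit question can tell us**

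| Question | Subject | Direction? | Names a single test? |
|---|---|---|---|
| 1 | Satisfaction with the whole year | Yes | No |
| 2 | Interest in the biomarker-based approach | Yes | No |
| 3 | Amount of change of mind, all three biomarkers together | No | No |
| 4 | Would recommend the approach | Yes | No |
| 5 | Free text on the process and future trial | Open | No |

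Items on a single named test: 0 of 5. Closed items with a direction: 3 of 4. Directional items on the biomarker approach: 2 (Questions 2 and 4), both for the package.

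**2. Question 3**

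Take one parent who began neutral and was won over, and one who began neutral and was put off by the pricks. Both can truthfully tick *Quite a lot*. Neither the monthly nor the exit form records an earlier opinion, so the direction of change cannot be recovered by comparison.

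**3. Interval between testing and the form**

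Inputs: 12 months' follow-up per child; recruitment of about 9 months (section 6); optional second test 3 months after the first (section 6); and the section 10 definition, "The end of the study will be when the last of the 100 participants completes his follow-up period of 12 months". Assumption: the first test falls close to enrolment.

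- Sent at each child's exit: about 12 months after the first test, and 12 − 3 = 9 months after the second.
- Sent at the defined end of study, for the first child recruited: 9 + 12 = 21 months after the first test. This agrees with the 20–21 months' total duration in section 6.

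The wording, "after the study is finished, to check their perspective and acceptability on these biomarkers", fits either reading, and Table 2 in Appendix 2 has no row for the exit form. The upper figure is itself uncertain, because section 2 gives 36 months' duration alongside dates that span 28 months.

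**4. What a per-test item would deliver**

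Illustration only; the count and the number of replies are assumptions. Wilson 95% interval, with p the observed proportion, n the replies and z = 1.96:

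[p + z²/(2n) ± z√(p(1−p)/n + z²/(4n²))] / (1 + z²/n)

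- 10 of 100 find a test unacceptable: (0.1192 ± 0.0619)/1.0384, giving 5.5% to 17.4%.
- 7 of 70: (0.1274 ± 0.0754)/1.0549, giving 4.9% to 19.2%.

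Either is precise enough to help in planning a trial. The plan as written produces no such estimate for any test.

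**The case against.** The strongest reply is that the exit form was never meant to carry the objective alone. Acceptability of the three tests is assigned to focus groups and one-to-one interviews, which can probe each test in depth. The interview guide is not in the documents, so nobody can say that per-test views will go uncollected. The form's own stated purpose is narrower, namely acceptability of using the biomarkers to guide therapy, and Questions 2 and 4 address that with a clear direction. The objective sets no rate, and qualitative feedback plus a short survey is a legitimate design for a feasibility study of 100 children.

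There is indirect evidence too. Uptake of the optional second test is a behavioural sign of acceptance, reasons for withdrawal are recorded where available (section 7.3), and Question 5 lets a parent criticise a particular test. Question 3 is one item among four, and no objective asks about change of opinion.

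Most of this stands. It defeats the inference that the acceptability objective cannot be answered, or that the later trial would have no basis for choosing between tests. That choice would also rest on each test's predictive value, which the study examines.

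It does not supply a number per test. Interviews yield themes from those who take part. The optional second test is described as one package, and its stated purpose is reproducibility. Free text captures only what a parent thinks to write.

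**Conclusion.** The point holds as a gap in measurement. No per-test quantitative acceptability measure is planned, although acceptability of the tests is both an aim and an objective. The one structured form arrives about 12 months after first testing, or up to about 21 months if it goes out at the defined end of study and first testing is close to enrolment. Its Question 3 cannot be interpreted for any parent who does not answer *Not at all*. Questions 2 and 4 remain usable for the package of three tests.

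A reader might also infer that the form misses families who leave early, so that the results come from the most willing. The documents do not say whether withdrawn families receive it. That silence should be resolved, but it is not evidence of exclusion, and no size can be put on any resulting bias without figures the documents do not give.

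This is an inexpensive improvement to a feasibility study. It does not undermine the study's design.

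**What to change.** 1. Give Question 3 a scale from much less favourable to much more favourable, with a neutral midpoint.
2. For each of the breath bag, skin prick and finger prick, add one acceptability item and one item asking whether the parent would agree to that test again. That makes 3 × 2 = 6 items.
3. Ask the six items on the existing electronic platform at the test visit and again at exit, and offer them at withdrawal.
4. State whether the exit form goes out when each child finishes or when the whole study ends, and add it to Table 2.
5. Add to section 11 that each item will be reported as a proportion with a 95% confidence interval, with the number of replies.

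The rewording in step 1 adds no burden. The new items mean 6 × 2 = 12 short answers for a family that completes the study, probably a few minutes in all, plus one extra contact at withdrawal and a small protocol amendment. Treatment and the tests themselves are unchanged.

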5.1. STUDY RISK / BENEFIT ANALYSIS

Benefits: The only tests of clinical significance to the child are the skin prick tests, which might for example inform a decision about the purchase of a pet. The family will be informed about these results. The other tests won't be of clinical significance. The ultimate benefit will be in the future if we can show with a large intervention trial that measuring one or more of these biomarkers helps predict future wheezing exacerbations as well as guide treatment more efficiently, thus children stop receiving unnecessary medications. The benefit generated by this trial is to show that these markers can be measured in practice, and they are acceptable to the families.

Risk analysis: Child participants' routine clinical management is not changed in this observational study. Clinicians have no access to study data. Risks relate to study procedures: all procedures [blood sampling through finger prick test, skin prick tests and FeNO collection (offline method)] will be performed by trained research personnel.

Skin prick tests are safe and used clinically for many years, but adrenaline and antihistamines will be available while the study procedures are being performed, in the highly unlikely event of an allergic reaction (Figure 1). All research staff will be trained in management of acute reactions / anaphylaxis. The finger prick test is the same as used by diabetic patients to monitor blood glucose. Collecting breath into a bag is devoid of risk.

[figure not shown]

Figure 1. Anaphylaxis case reports after skin prick test. (A) Clinical study in Cambridge, UK involving 31,000 participants (17), (B) Retrospective analysis from 4 allergy centres in Italy (Verona, Genoa and Naples) involving 55,105 participants (18).

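### Exit Question 4 has no mild negative answer, so it blurs parents' opposition and can understate it; use a balanced five-point scale

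*Combined protocol and SAP*

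**What the plan says.** Acceptability is part of the study's purpose. The aim in Section 5 ends "Also, that these tests are acceptable to families", and one objective is "To evaluate the feasibility and acceptability of these tests". Section 5.1 describes the benefit of the study as showing that "these markers can be measured in practice, and they are acceptable to the families". Section 4.3 lists acceptability among the things to be settled before a large randomised trial.

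Sections 6 and 7.1 name the exit questionnaire as a tool for this. They say that it covers parents' views on biomarkers guiding treatment in future. Focus groups and one-to-one interviews are the other source.

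The items in Appendix 5 are:

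- **Question 1** (satisfaction with the one-year study): five points, from "Very Dissatisfied" through neutral to its mirror image.
- **Question 2**, "Question 2: As a parent would you be interested in having the biomarker-based approach for your child in the future": *Yes*, *No* or *Maybe*.
- **Question 3**: how far the study changed the parent's mind, with no direction recorded.
- **Question 4**, printed as "Question 4: Would you recommend this approach to other parents with children experiencing the same wheezing conditions": *Not at all*, *Maybe*, *Recommend* or "Highly recommend".
- **Question 5**: free text, including "Would you change anything on the current process? What was good, what was not good".

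Section 11 does not say how Question 4 is scored, which answers count as acceptance, or what summary will be reported.

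**The concern.** Support in Question 4 comes in two strengths, while opposition comes only in its strongest form. A parent who would probably not recommend the approach finds no matching answer. Whichever box that parent ticks, information is lost: *Not at all* merges mild with firm refusal, and *Maybe* merges mild refusal with indecision.

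Only Questions 2 and 4 ask directly for or against the biomarker approach, and only Question 4 grades the reply. It is therefore the one item on the form that could show how strongly parents lean each way, and it cannot do so on the negative side. For a feasibility study that must report whether families accept the approach, the size of mild reluctance is worth knowing before a larger trial is designed. The balanced format of Question 1 shows that the imbalance is not forced by the layout.

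**Working it through.** The plan states no figure for this item, so there is nothing to reproduce. The check is a count of the options, followed by an illustration.

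**Option count (Appendix 5)**

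| Item | Unfavourable | Neutral or ambiguous | Favourable |
|---|---|---|---|
| Question 1 | 2 | 1 | 2 |
| Question 2 | 1 | 1 | 1 |
| Question 4 | 1 (extreme) | 1 | 2 |

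**Illustration.** Take 100 parents, matching the 100 children in Section 5. The rest is assumed: 5 strongly against, 15 neutral, *m* mildly against with *m* = 5, 10 or 20, and the remainder favourable, split equally between the two grades.

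- Favourable = 100 − 5 − 15 − *m* = 80 − *m*.
- Unfavourable on a balanced scale = 5 + *m*.
- Unfavourable on Question 4 = 5 + (the number of the *m* who tick *Not at all*).

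| *m* | Favourable, balanced | Favourable, Question 4, no opponent ticks a favourable box | Unfavourable, balanced | Unfavourable, Question 4, all *m* tick *Maybe* | Unfavourable, Question 4, all *m* tick *Not at all* |
|---|---|---|---|---|---|
| 5 | 75% | 75% | 10% | 5% | 10% |
| 10 | 70% | 70% | 15% | 5% | 15% |
| 20 | 60% | 60% | 25% | 5% | 25% |

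Recorded opposition falls short by between 0 and *m* points, so by 0 to 20 points over the range assumed. The favourable share stays the same in every row.

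**When would acceptance be overstated?**

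1. *If everything except Not at all counts as acceptance.* With *m* = 10 and all ten ticking *Maybe*, the figure is 100 − 5 = 95%. On a balanced scale, the share not against would be 100 − 15 = 85%. The rise equals the mildly opposed share.
2. *If some opponents tick Recommend.* If one in ten does (assumed), the favourable share rises by 0.1 × *m*: from 75% to 75.5%, 70% to 71%, and 60% to 62%.
3. *If answers are averaged on a 0 to 1 scale.* With *m* = 10, the balanced scale gives (0×5 + 0.25×10 + 0.5×15 + 0.75×35 + 1×35)/100 = 0.713. Question 4 with all ten at *Maybe* gives (0×5 + ⅓×25 + ⅔×35 + 1×35)/100 = 0.667. With all ten at *Not at all* it gives (0×15 + ⅓×15 + ⅔×35 + 1×35)/100 = 0.633. The mean falls, because *Maybe* sits at one third on a four-point scale.

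So the direction of any bias in an acceptance figure depends on a scoring rule that the plan does not contain.

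**The case against.** The strongest reply is that a reader might infer that the scale pushes the acceptability result upwards, and that the documents do not show this. The reply is right. The favourable share does not move unless opponents choose a favourable answer, and a mean score can fall. Section 11 defines no acceptability figure that could be biased. Nor do the documents attach a progression criterion or threshold to Question 4.

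It is also fair to say that mildly opposed parents are not silenced. They may tick *Not at all*, answer *No* or *Maybe* to Question 2, write in Question 5, or speak in an interview. These outlets reduce the consequence but do not restore the missing grade. The *No* in Question 2 has no strengths, and the free text and interviews give themes rather than a distribution over all parents.

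A second tempting inference is that *this approach* is ambiguous between having the three tests and having treatment guided by them, and that the item should ask only about the tests. The documents do not support that change. Question 2 names the biomarker-based approach, Question 3 speaks of personalising treatment, and Sections 6 and 7.1 say that the form concerns biomarkers guiding therapy. Read in sequence, Question 4 means biomarker-guided care.

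**Conclusion.** The point holds as a measurement weakness in one item. Question 4 is unbalanced, so it blurs opposition and can understate it by anything from none to all of the mildly opposed share. The range of 0 to 20 points rests on the assumption that 5 to 20 of 100 parents are mildly against; the documents give no basis for a narrower figure. Where in the range the result falls depends on how those parents divide between *Maybe* and *Not at all*, which the completed form cannot reveal.

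Overstated acceptance is a conditional risk. It arises if *Maybe* is counted as acceptance or if some opponents tick a favourable box. Severity is low: the item is descriptive, has other sources of acceptability data beside it, and does not touch the primary outcome.

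**What to change.** Replace the four answers with a balanced set: definitely not, probably not, unsure, probably, definitely. Keep the question on the biomarker-guided approach named in Question 2, and report the full distribution rather than a single share.

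If the form has already been used, report all four categories separately and do not count *Maybe* as acceptance.

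The change affects one electronic item and needs no extra contact with families. It does alter a protocol appendix, and Section 17 requires prior Sponsor and HRA approval for departures from the protocol, so a small amendment should be expected.
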